2. BACKGROUND AND RATIONALE

Every year more than 1 million PCIs are performed in United States and similar numbers in Europe^{1,2}. In more than 85% of cases a coronary stent is implanted³, with the ensuing need for prolonged antiplatelet therapy in order to prevent stent thrombosis (ST). The international Practice Guidelines recommend dual antiplatelet therapy (DAPT) with aspirin and a P2Y₁₂ receptor antagonist for at least one month after bare metal stent (BMS) implantation and for 6 months after drug eluting stent (DES)^{4,5}. In patients with acute coronary syndrome (ACS), DAPT should be prolonged up to 12 months.

Premature discontinuation of antiplatelet therapy is associated with a significant increase in the risk of ST⁶⁻⁹, an infrequent but lifethreatening event which occurs most of the times as acute myocardial infarction (MI), with a mortality rate of 10-40%. The single most important predictor of ST is the cessation of antiplatelet therapy¹⁰⁻¹². Previous studies demonstrated that premature discontinuation of antiplatelet therapy (permanent or transitory) after stent implantation occurs in 10-50% of patients^{7,13}, most frequently due to surgical interventions¹³.

It has been estimated that 4-8% of patients submitted to stent implantation undergo surgery within the first year³. The perioperative management of antiplatelet therapy represents a relevant issue, not only as it is epidemiologically relevant, but also because it may have significant clinical consequences¹⁷. A patient who experiences a perioperative MI has an inhospital mortality of 15-25%¹⁸⁻²⁰.

Perioperative management of antiplatelet therapies raises important challenges and safety concerns. On one hand, withholding therapy to reduce the risk of bleeding complications is associated with a heightened risk of ischemic events, including life-threatening stent thrombosis (ST), myocardial infarction (MI) and stroke [8-10]. Surgery leads to inflammatory, hypercoagulable and hypoxic states which are associated with plaque instability and perioperative

arterial thrombosis^{3,14}. Thus, the perioperative risk of ST and other cardiac ischemic events is high, particularly if antiplatelet therapy is discontinued^{15,16}. On the other hand, maintaining antithrombotic therapy may increase the risk of bleeding and the need for transfusions, which are both known determinants of poor prognosis [3-10].

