4.3 Secondary endpoints

Patients undergoing non cardiac surgery:

- The composite of death, myocardial infarction, probable/definite stent thrombosis according the Academic Research Consortium definition⁴⁴ and bleeding events of Bleeding Academic Research Consortium (BARC) grade ≥ 3 at 30 days
- The composite of death, myocardial infarction and probable/definite stent at 30 days
- The incidence of bleeding events of Bleeding Academic Research Consortium (BARC) grade ≥ 3 at 30 days
- The type and the length of discontinuation of any antiplatelet therapy in patients undergoing non cardiac surgery according to time from PCI to surgery
- Rate of non cardiac surgical procedures within 12 months from PCI divided into quartiles (0-3, 3-6, 6-9, 9-12 months)
- Delay in performing non cardiac surgical procedure

Patients undergoing cardiac surgery:

- The composite of death, myocardial infarction, probable/definite stent thrombosis according the Academic Research Consortium definition⁴⁴ and bleeding events of Bleeding Academic Research Consortium (BARC) grade ≥ 4 at 30 days
- The composite of death, myocardial infarction and probable/definite stent at 30 days
- The incidence of bleeding events of Bleeding Academic Research Consortium (BARC) grade ≥ 4 at 30 days
- The type and the length of discontinuation of any antiplatelet therapy in patients undergoing cardiac surgery according to time from PCI to surgery
- Rate of cardiac surgical procedures within 12 months from PCI divided into quartiles (0-3, 3-6, 6-9, 9-12 months)
- Delay in performing cardiac surgical procedure

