For each patient, surgical hemorrhagic and thrombotic risk (according to the SAS 2 Consensus Document definitions) will be identified at the time of data analysis according to clinical and angiographic characteristics that will be captured in the eCRF.

Outcome Events

The following outcome events will be captured by the eCRF:

- Death

- Myocardial infarction, recurrent ischemia, heart failure, ventricular tachycardia, ventricular fibrillation.
- Major bleeding
- Transfusions
- Reoperation due to bleeding

See point 8 for definitions

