6.4 Bleeding Classification

All bleeding events will be considered in patients undergoing cardiac and non cardiac surgery.

Bleeding events will be classified according to BARC classification.

Bleeding Academic Research Consortium Definition for Bleeding (Ref 43)

- Type 0: no bleeding
- Type 1: bleeding that is not actionable and does not cause the patient to seek unscheduled performance of studies, hospitalization, or treatment by a healthcare professional; may include episodes leading to self-discontinuation of medical therapy by the patient without consulting a healthcare professional

- Type 2: any overt, actionable sign of hemorrhage (eg, more bleeding than would be expected for a clinical circumstance, including bleeding found by imaging alone) that does not fit the criteria for type 3, 4, or 5 but does meet at least one of the following criteria: (1) requiring nonsurgical, medical intervention by a healthcare professional, (2) leading to hospitalization or increased level of care, or (3) prompting evaluation

- Type 3

Type 3a: overt bleeding plus hemoglobin drop of 3 to <5 g/dL* (provided hemoglobin drop is related to bleed); any transfusion with overt bleeding

Type 3b: overt bleeding plus hemoglobin drop ≥ 5 g/dL* (provided haemoglobin drop is related to bleed); cardiac tamponade; bleeding requiring surgical intervention for control (excluding dental/nasal/skin/hemorrhoid); bleeding requiring intravenous vasoactive agents

Type 3c: intracranial hemorrhage (does not include microbleeds or hemorrhagic transformation, does include intraspinal); subcategories confirmed by autopsy or imaging or lumbar puncture; intraocular bleed compromising vision

- Type 4: CABG-related bleeding, including perioperative intracranial bleeding within 48 h, reoperation after closure of sternotomy for the purpose of controlling bleeding, transfusion of >5 U whole blood or packed red blood cells within a 48-h period, chest tube output >2L within a 24-h period
- Type 5: fatal bleeding

Type 5a: Probable fatal bleeding; no autopsy or imaging confirmation but clinically suspicious

Type 5b: Definite fatal bleeding; overt bleeding or autopsy or imaging confirmation

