APPENDIX A: SCHEDULE OF PROCEDURES

Procedures	Screening	Index admission	Discharge	1 month
Informed consent	X			
Demographics	X			
Medical history	X			X
Concomitant medications	X	X	X	X
Physical examination	X	X		
ECG	X	X	X	
Laboratory tests: blood cell count	X	X	X	
Eligibility assessment	X			
Compliance with medications				X
Assessment 1			Report of MACCE and bleeding during index admission	
Assessment 2 and following				Report of MACCE and bleeding
Adverse event assessments		X	X	X

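### Non-fatal ischaemic stroke, which the background names as a risk of withholding therapy, has no eCRF outcome item, no definition and no place in any endpoint, although Appendix A asks sites for undefined MACCE reports

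*Combined protocol and SAP*

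**What the plan says.** Section 2 (Background and Rationale) says that withholding therapy carries a "heightened risk of ischemic events, including life-threatening stent thrombosis (ST), myocardial infarction (MI) and stroke". Section 3.2 makes ischaemic and haemorrhagic events a secondary objective.

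The outcome list in section 4.5.3 has a line for death, a line reading "Myocardial infarction, recurrent ischemia, heart failure, ventricular tachycardia, ventricular fibrillation", and lines for major bleeding, transfusions and reoperation for bleeding. Neither stroke nor stent thrombosis is itemised. The list sends the reader to point 8 for definitions, but section 8 is quality control; the definitions are in section 6.

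Section 4.3 builds the net composite, for each type of surgery, from "The composite of death, myocardial infarction, probable/definite stent thrombosis according the Academic Research Consortium definition" plus BARC bleeding. The ischaemic composite is the same without bleeding. The bleeding endpoint for non-cardiac surgery is "The incidence of bleeding events of Bleeding Academic Research Consortium (BARC) grade ≥ 3 at 30 days"; for cardiac surgery it is "The incidence of bleeding events of Bleeding Academic Research Consortium (BARC) grade ≥ 4 at 30 days". Section 6.4 places intracranial bleeding in "Type 3c: intracranial hemorrhage (does not include microbleeds or hemorrhagic transformation, does include intraspinal".

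In section 6, stroke appears only in 6.2, as a cause of cardiovascular death. Appendix A schedules "Report of MACCE and bleeding during index admission", a second MACCE and bleeding report at 1 month, and adverse event assessments at three time points.

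**The concern.** The registry is meant to set ischaemic harm against bleeding harm when antiplatelet therapy is managed by the SAS 2 document or by local practice. By the protocol's own rationale, stroke belongs on the ischaemic side. As written, a patient who survives an ischaemic stroke after an interruption is an event in neither composite.

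Appendix A makes this an inconsistency as well as a choice of endpoint. Sites are asked to report MACCE, a term that is usually read as including cerebrovascular events, but the outcome list offers no stroke field and the protocol does not say what MACCE contains. Sites may therefore record strokes in different ways or not at all, and the analysis would have no agreed definition with which to sort them.

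**Working it through.** This is a question of what the endpoints contain, so the main check is to set the sections side by side.

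**1. Where each event counts (non-fatal events, thresholds of section 4.3)**

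| Event | Itemised in 4.5.3 | Defined in section 6 | Net composite, non-cardiac (BARC ≥ 3) | Net composite, cardiac (BARC ≥ 4) |
|---|---|---|---|---|
| MI | yes | yes | yes | yes |
| Definite/probable stent thrombosis | no | yes, by reference to ARC | yes | yes |
| Ischaemic stroke | no | no | no | no |
| Intracranial haemorrhage | only as major bleeding | yes, BARC 3c | yes | only if type 4 (CABG-related, within 48 h) |

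Fatal stroke of either kind counts through all-cause death. Haemorrhagic transformation of an ischaemic stroke is excluded from type 3c, so it does not enter by that route.

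**2. BARC thresholds.** Section 4.3 uses ≥ 3 for non-cardiac and ≥ 4 for cardiac surgery. Section 7.2 states the reverse. Under 7.2, type 3c would leave the non-cardiac bleeding analysis and enter the cardiac one. On either reading, one surgical population counts a non-fatal intracranial haemorrhage and not a non-fatal ischaemic stroke; which population depends on which section governs.

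**3. Other routes into the database.** Section 4.5.4 collects any adverse events and new hospitalisations by questionnaire at 30 days. Appendix A schedules the MACCE reports and adverse event assessments. Section 11.2 has the committee adjudicate critical adverse events. A stroke could arrive by any of these. None gives a definition, a type or a dedicated field. The term critical is not defined, and the 4.5.4 check of endpoint items does not reach stroke, because stroke is not an endpoint. MACCE is absent from the abbreviations list and does not match the MACE and NACE of section 7.2, which are also undefined.

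**4. Size.** The only relevant figure in the plan is N = 1,623 (section 7.1). It cannot be reproduced, because no event rates or effect size are given, but this point does not depend on it. Uncounted events = rate × N. The 30-day rate of non-fatal ischaemic stroke is my assumption:

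- 0.3%: 0.003 × 1,623 = 4.9
- 1.0%: 0.010 × 1,623 = 16.2

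This is a count over both groups. The effect on a group comparison depends instead on the between-group difference in stroke risk among patients with no other component event. If that difference is 0, the omission changes the risk difference in the composite by 0; if it is 1.0 percentage point (again assumed), by 1.0 point. The sign follows whichever group has more strokes.

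For scale, take the 324 and 162 patients of section 7.1 and the usual two-proportion normal approximation at two-sided 5%. With 10% in the group of 162, 80% power needs about 19.8% in the group of 324, a gap of 9.8 points. An assumed shift of up to 1.0 point is small beside that.

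**The case against.** The strongest reply has four parts.

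- **Capture.** A reader might infer from the 4.5.3 list that strokes are not recorded and cannot be recovered at analysis. The documents do not support that: the MACCE reports, the adverse event assessments, the 30-day questionnaire and adjudication of critical events are all plausible routes. What remains is that capture is undefined and likely to vary between sites.
- **Direction.** It is tempting to say that the net composite is tilted against continuing therapy, because intracranial bleeding counts and ischaemic stroke does not. The comparison, however, is SAS 2 management against local practice, and SAS 2 itself includes wash-out and bridging for some operations. No stroke or interruption rates by group are given. The composite also keeps death, MI and stent thrombosis as ischaemia-sensitive components. A directional bias is not shown. It remains true that discontinuation without bridging is the primary endpoint, so it is the behaviour the groups are expected to differ on, and stroke is an outcome the protocol ties to it.
- **Asymmetry.** Type 3c is in the net composite only for non-cardiac surgery under 4.3, and 7.2 contradicts even that. The asymmetry cannot be claimed for both composites.
- **Choice of endpoint.** Restricting the composites to death, MI and stent thrombosis is a legitimate coronary-stent choice. That is a reason to leave them as they are and to report stroke alongside them; it does not explain an undefined MACCE report.

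Stent thrombosis is a lesser matter. It is defined in section 6, and 4.5.4 asks for endpoint items, so its absence from the 4.5.3 list is a matter of alignment.

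**Conclusion.** The point holds as one of consistency and completeness, and should be addressed. Non-fatal ischaemic stroke is a harm the protocol names, yet it is not itemised, not defined and in no endpoint, while Appendix A calls for a MACCE report that the outcome list does not support. Followed as written, the plan leaves this harm out of the comparison of ischaemia with bleeding.

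The size is not established. The 5 to 16 uncounted events rest wholly on the assumed 0.3% to 1.0%, and the effect on the group difference could be zero or of either sign. The primary endpoint, antiplatelet discontinuation, is unaffected. Which population shows the intracranial haemorrhage asymmetry cannot be settled until sections 4.3 and 7.2 agree.

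**What to change.** 1. In section 4.5.3, add a dated stroke item (ischaemic / haemorrhagic / undetermined) to the outcome list, and list definite/probable stent thrombosis there to match 4.3.
2. In section 6, define stroke and MACCE, and align the terms in 4.5.3, 7.2 (MACE, NACE) and Appendix A. Correct the pointer in 4.5.3 so that it leads to section 6.
3. Send every suspected stroke to the Event-adjudication Committee.
4. Reconcile the BARC thresholds for cardiac and non-cardiac surgery between 4.3 and 7.2.
5. In 4.3, add 30-day ischaemic stroke by group as a secondary endpoint for both types of surgery, and report each composite a second time with ischaemic stroke included. The existing composites stay unchanged.

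The cost is a few eCRF fields, short definitions, some extra adjudications (about 5 to 16 ischaemic strokes under the assumed rates, plus other suspected cases) and one extra table row per composite. No new tests or visits are needed. Prospective capture is more reliable than reconstructing strokes later from generic adverse event reports.

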4.5.4 Follow-up

A follow-up contact visit is planned at 30 days (\pm 7 days) after the surgical procedure using hospital records, outpatient visits, or telephone contact. A standard questionnaire will be used to collect information on the medications the patients were taking and the occurrence of any adverse events. Each site will have a designated individual who entered raw data into an electronic case report form, allowing immediate and continuous monitoring of its completeness and accuracy. Unscheduled visits can also take place whenever necessary.

Relevant information to be inquired and collected in the e-CRF will include:

- check of items describing the primary and secondary study endpoints, with special reference to new hospitalizations;
- ongoing medications
- compliance with medication prescribed at discharge
- adverse events

4.6 Source Data

When required for the adjudication of endpoint clinical events, original documents, data, and records from which participants' CRF data are obtained will be electronically uploaded in the

eCRF (see point 9). These include, but are not limited to, hospital records (from which medical history and previous and concurrent medication may be summarised into the CRF), clinical and office charts, laboratory and pharmacy records, diaries, radiological images.

5. TREATMENT OF PARTICIPANTS

The Registry will record actual perioperative management strategies in patients with previous stent implantation undergoing surgical and operative endoscopic/endovascular procedures. A guidance for the perioperative management of antiplatelet therapy is provided by the Consensus Document SAS 2 issued by GISE. The document is enclosed as an Appendix to the present protocol. The recommendations can be accessed by the Investigators through a workable web application, which can be downloaded at <https://itunes.apple.com/us/app/stent-surgery/id551350096?mt=8>.

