the relative merit of a risk stratification approach for both ischemia and bleeding in patients with coronary stents undergoing cardiac and NCS [21]. However, the landscape of devices, antithrombotic drugs, and surgical techniques has changed over the past years. In particular, the advent of the newer generation of DES has been associated with a remarkable risk reduction of ST, potentially allowing for a safe shorter DAPT duration, particularly in low ischemic risk patients [12, 22, 23]. On the other hand, data have shown potential for a protective effect of prolonged DAPT duration in high-risk settings [12, 22, 23]. The POISE-2 trial, investigating the effects of perioperative aspirin use, showed that this had no significant effect on the combined risk of death or nonfatal MI in patients undergoing non-cardiac surgery [24]. Nevertheless, it is important to note that only one patient out of four in this study had a history of coronary artery disease and only 4% of randomized patients had previously received coronary stents. Moreover, patients with implantation of DES within 1 year and BMS <6 weeks were excluded. Due to this limitation, the results of the POISE-2 trial should not be applied to patients with previous coronary stent implantation. Thus, while being an important study, it should not be considered when managing perioperative antiplatelet therapy in patients with coronary stents undergoing surgery.

The SAS 2 Consensus Document derives from a multidisciplinary collaboration and provides practical recommendations on the perioperative management of antithrombotic therapy in patients treated with coronary stents. These recommendations are summarized in the present document and can be accessed through a workable web application, which can be downloaded at <https://itunes.apple.com/us/app/stent-surgery/id551350096?mt=8>. The Writing Committee was composed of cardiologists, surgeons, anesthesiologists, and hematologists. Overall, the recommendations summarized in this document were finally endorsed by 23 scientific societies, including interventional cardiology (n=1), anesthesiology (n=1), hematology (n=1), and a number of surgical specialties (n=20).

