4. STUDY DESIGN

4.1 Summary of Study Design

The SAS registry will include any patient with previous coronary stenting undergoing any type of surgery or operative endoscopic/endovascular procedure at the participating Centers. Centers will be divided into two groups: Centers that routinely follow the recommendations of the SAS 2 Document and Centers that do not. The relevant clinical, procedural and outcome data (within index admission and at 30 days) will be entered in a specifically designed electronic case record form (eCRF).

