7. STATISTICS

7.1 The Number of Participants

Consecutive patients will be enrolled over one year of time at the participating Centers.

Cases and controls patients will be divided into those who will use Consensus Document “Stent and Surgery-2” (group 1) vs those who traditionally will be managed by local practice (group 2). On the basis of previous data reported SAS, a sample size of 1623 patients would be required to have a case-control matching 1:2, assuming a study power of 80% and 5% significance. Of those, 324 case-patients (20% of group 1) vs 162 control-patients (ratio 1:2) would be required for enrollment within one-year after implanted stents. Two preplanned interim analyses will be performed by an independent statistician when 800 and 1500 of patients will be enrolled.

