7.2 Description of Statistical Methods

Continuous numeric variables will report as means with SD and compared using the Student’s t- or Wilcoxon rank-sum test. Categorical variables will be presented as counts and percentages and will be compared using the chi-square or Fisher’s exact test. To examine the effect of significant factors on two different groups (Group 1 vs Group 2) the hazard ratio of the interaction term will be calculated. To identify the independent predictors for in hospital NACE, 30day MACE and 30-day BARC bleedings, first univariate and then multivariate logistic regression models will apply. The BARC bleedings will be considered according to type of surgery. Specifically, BARC bleedings grade ≥ 3 will be considered in patients undergoing cardiac surgery, and BARC bleedings grade ≥ 4 will be taken into account for non-cardiac surgery. Covariates for multivariable models will be selected on the basis of a backward stepwise algorithm in a Cox proportional hazards model. Additionally, to minimise group differences on confounding covariates between patients who will be managed with consensus document (group 1) and those who will be received local practice (group 2), a 1:2 propensity score matching would be used. Propensity scores will be calculated with logistic regression, with multiple imputation and backwards elimination with a significance level to stay of 0.05. To ensure that the comparison between two groups (group 1 vs group 2) would not be bias, the proportion of patients who will not received consensus document within center that traditionally used it, will be excluded. The results will be presented as ORs with 95% confidence intervals (CI) and p values. For all

analyses, a two-sided $P <0.05$ will be required for statistical significance. All data will be analyzed using the Statistical Package of Social Sciences version 20 (IBM SPSS, Chicago, IL).

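### Crossover is handled in one direction only: SAS 2 use in local-practice centres is neither recorded nor addressed, although the protocol offers SAS 2 to investigators without limit by centre group

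*Combined protocol and SAP*

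**What the plan says.** **How the groups are formed.** Section 4.1 groups by centre: "Centers will be divided into two groups: Centers that routinely follow the recommendations of the SAS 2 Document and Centers that do not". Section 7.1 words the same contrast by patient, setting those who will use SAS 2 (group 1) against those managed by local practice (group 2).

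**Who is given SAS 2.** Section 5 names SAS 2 as the available guidance on perioperative antiplatelet therapy and states "The document is enclosed as an Appendix to the present protocol". It adds "The recommendations can be accessed by the Investigators through a workable web application". Neither statement is limited to group 1 centres. The same section opens by saying "The Registry will record actual perioperative management strategies in patients with previous stent implantation", so it does not require anyone to follow SAS 2.

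**How crossover is handled.** Section 7.2 gives one rule: "the proportion of patients who will not received consensus document within center that traditionally used it, will be excluded". It has no rule for a group 2 patient managed with SAS 2.

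**What is recorded.** The eCRF items in Sections 4.5.3 and 4.5.4 include the antiplatelet and bridging drugs, and dates and times of stopping and restarting. SAS 2 bleeding and thrombotic risk is to be assigned at analysis. Whether SAS 2 was consulted or applied for the case is not listed.

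**The concern.** The primary endpoint (Sections 4.2 and 6.1) is antiplatelet discontinuation without bridging. That is the behaviour SAS 2 advises on, so any uptake in group 2 acts directly on the primary outcome. Patients are screened at preoperative evaluation by the cardiologist together with the anaesthesiologist, surgeon or endoscopist (Section 4.5.2), who are the clinicians SAS 2 addresses.

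Two things are at stake. First, a null result would be hard to interpret: SAS 2 might make no difference, or group 2 might have used it too. Section 2 says the impact of SAS 2 in practice has not been evaluated, so this is the question the registry exists to answer. Second, the Section 7.2 exclusion depends on knowing, patient by patient, whether SAS 2 was used, and no listed data item supplies that.

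**Working it through.** **Step 1. Crossover, direction by direction.**

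| Patient | Planned handling | Listed item that identifies the patient |
|---|---|---|
| SAS 2 centre, managed by SAS 2 | Kept in group 1 | None |
| SAS 2 centre, not managed by SAS 2 | Excluded (Section 7.2) | None |
| Local-practice centre, not managed by SAS 2 | Kept in group 2 | None |
| Local-practice centre, managed by SAS 2 | Not stated | None |

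The last row is the gap. By Section 4.1 the patient stays in group 2. By the patient-level wording of Section 7.1 the same patient could count as group 1.

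**Step 2. Direction of bias.** Suppose a share c of group 2 is managed, and fares, as group 1 does. The group 2 rate then moves from p2 to p2 - c(p2 - p1), and the contrast becomes (1 - c) times the planned one. Taken alone, this pulls towards no difference. The Section 7.2 exclusion is a separate force. If, for example, urgent cases are the ones in which SAS 2 is not consulted, they leave group 1 while comparable cases stay in group 2. That could enlarge, shrink or reverse the contrast, so the net direction is not determined.

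**Step 3. The plan's own figure.** Section 7.1 states "a sample size of 1623 patients would be required to have a case-control matching 1:2, assuming a study power of 80% and 5% significance". No control rate, effect size or dropout is given, so 1623 cannot be reproduced and no loss of power can be derived from the documents alone. The split is also unclear. The 324 cases are called 20% of group 1, but 20% of the total is 0.20 × 1623 = 324.6. A 1:2 split of 1623 gives groups of 541 and 1082, and 20% of those is 108.2 or 216.4. The pair 324 and 162 is 2:1 case to control. I therefore ran 541/1082 and 162/324, each in both directions.

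**Step 4. Sensitivity, on assumptions only.**

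- From the documents: power 80%, two-sided 5%, the group sizes above.
- Assumed: control rates from 10% to 50%; uptake c of 10%, 20% or 30%; SAS 2-managed controls have group 1's outcome rate.
- Method: for each control rate, solve for the group 1 rate that gives 80% power in a two-proportion test (pooled variance under the null), then recompute power with the diluted control rate.

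Example with 541 controls, 1082 SAS 2 patients and a control rate of 30%: a group 1 rate of 23.51% gives 80% power, a difference of 6.49 points. With c = 20%, the control rate becomes 30 - 0.2 × 6.49 = 28.70%, and the difference is 5.19 points. The standard error is 0.02287 under the null and 0.02333 under the alternative. Power = Phi((0.0519 - 1.96 × 0.02287)/0.02333) = Phi(0.30), about 62%.

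The constant-variance approximation is Phi(2.80(1 - c) - 1.96). It gives the low end of each range.

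| Assumed uptake c | Contrast left | Approximation | Range over splits and control rates | Total N to restore 80%, from 1623 |
|---|---|---|---|---|
| 10% | 0.90 | 71% | 71-74% | 1955-2004 |
| 20% | 0.80 | 61% | 61-66% | 2411-2532 |
| 30% | 0.70 | 50% | 50-58% | 3063-3306 |

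The power ranges cover all four splits; the sample sizes cover the two splits of 1623.

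**The case against.** **The control group is not shown to be contaminated.** A reader might infer from Section 5 that it is, and that the contrast does shrink. The documents do not support that. Access is not adoption, the registry records what clinicians actually do, and nothing tells group 2 centres to use SAS 2. That every local-practice centre is handed the document is itself inferred from undifferentiated wording. Occasional use at a centre that does not routinely follow SAS 2 also fits the Section 4.1 definition of group 2. This objection stands: the point is an unaddressed risk, not a demonstrated fault.

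**Uptake would not be wholly invisible.** Drug dates, bridging (Sections 4.5.3 and 6.1) and SAS 2 risk class could be used to derive concordance with SAS 2 in both groups. This stands in part. Concordance does not show whether SAS 2 was used or local practice happened to agree with it, and no concordance analysis is planned.

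**Withholding the appendix from group 2 would do little.** Section 2 already says the recommendations "can be accessed through a workable web application, which can be downloaded at" a public address and summarises the advice, and Section 6.1 repeats the bridging advice. This stands, and I do not propose that restriction.

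**The power figures are illustrative.** This stands too. The uptake shares have no source in the documents, and the calculation leaves out the exclusion and confounding between centres.

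What survives is the asymmetry. The plan treats patient-level SAS 2 use as important enough to exclude on in group 1, yet neither records it nor deals with it in group 2.

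**Conclusion.** The point holds as a gap in design and analysis that should be closed. Section 5 offers SAS 2 without regard to centre group, Section 7.2 deals with crossover in one direction only, and the item that rule needs is not among those listed. Group 2 uptake would dilute the primary contrast; the one-sided exclusion could bias it either way.

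The size cannot be established from the documents. The falls to about 71-74%, 61-66% and 50-58% are conditional on uptake of 10%, 20% and 30%, control rates of 10-50%, and SAS 2-managed controls behaving exactly like group 1. They show that modest uptake would matter; they do not predict that it will occur.

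**What to change.** 1. Classify each centre from practice documented before it receives the protocol, and state in Section 4.1 that the classification is then fixed.
2. Add one eCRF item for every patient in both groups: was SAS 2 (document or app) used for this case?
3. Make the by-centre comparison of all enrolled patients the primary one, and align the group wording in Section 7.1 with Section 4.1. Move the Section 7.2 exclusion to a sensitivity analysis.
4. Report how often SAS 2 was used in group 2. Add sensitivity analyses by recorded use and by concordance derived from data already captured. Do not simply drop SAS 2-managed controls, since that could add selection bias of its own.

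**Cost.** One data item and a little more analysis, with no change to patient care. The item may be misreported, and analyses by recorded use remain open to confounding by the reasons for consulting SAS 2. The by-centre contrast may be smaller once non-users are kept in group 1. The item needs to be in place before enrolment, because consultation cannot be reliably reconstructed afterwards.
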